7.5.1.2.1 Seriousness

For each AE, the seriousness must be determined according to the criteria given in Section 7.5.1.1.

7.5.1.2.2 Intensity

The severity (or intensity) of adverse events should be graded according to NCI-CTCAE v4.03. If no exact matching code is available in CTCAE v4.03 then use the following guide:

- CTC 1 = Mild AE, transient in nature and generally not interfering with normal activities
- CTC 2 = Moderate AE, sufficiently discomforting to interfere with normal activities
- CTC 3 = Severe AE, prevents normal activities
- CTC 4 = Life-threatening and/or disabling AE
- CTC 5 = Results in death (fatal)

Phase II Study of Perindopril and Regorafenib in mCRC (PARICCA)

7.5.1.2.3 Causal relationship

The assessment of the causal relationship between an AE and the administration of treatment is a clinical decision based on all available information at the time of the completion of the CRF. The causality assessment should be done separately for each study treatment as detailed in the CRF.

The assessment is based on the question whether there was a “reasonable causal relationship” to the study treatment in question.

Possible answers are “yes” or “no”

An assessment of “no” would include:

1. The existence of a clear alternative explanation, e.g. mechanical bleeding at surgical site.

or

2. Non-plausibility, e.g. the subject is struck by an automobile when there is no indication that the drug caused disorientation that may have caused the event; cancer developing a few days after the first drug administration.

An assessment of “yes” indicates that there is a reasonable suspicion that the AE is associated with the use of the study treatment.

- Factors to be considered in assessing the relationship of the AE to study treatment include:
- The temporal sequence from drug administration: The event should occur after the drug is given. The length of time from drug exposure to event should be evaluated in the clinical context of the event.
- Recovery on drug discontinuation (de-challenge), recurrence on drug re-introduction (re-challenge)
- Subject’s response after de-challenge or subjects response after re-challenge should be considered in the view of the usual clinical course of the event in question.
- Underlying, concomitant, intercurrent diseases: Each event should be evaluated in the context of the natural history and course of the disease being treated and any other disease the subject may have.
- Concomitant medication or treatment: The other drugs the subject is taking or the treatment the subject receives should be examined to determine whether any of them may be suspected to cause the event in question.

7.5.1.2.4 Action taken with study treatment

Any action on study treatment to resolve the AE is to be documented using the categories listed below.

The study treatment action should be recorded separately for each study treatment as detailed in the CRF.

- Drug withdrawn
- Drug interrupted

Phase II Study of Perindopril and Regorafenib in mCRC (PARICCA)

- Dose reduced
- Dose not changed
- Dose increased
- Not applicable
- Unknown

Treatments administered specifically because of the adverse event should be recorded using the categories below:

- None
- Remedial drug therapy
- Other

7.5.1.2.6 Outcome

The outcome of the AE is to be documented as follows:

- Recovered/resolved
- Recovering/resolving
- Recovered/resolved with sequelae
- Not recovered/not resolved
- Fatal
- Unknown

7.5.1.3 Assessments and documentation of adverse events

All adverse events occurring after the subject has signed the informed consent must be fully recorded in the subject's case record form.

Documentation must be supported by an entry in the subject's file. A laboratory test abnormality considered clinically relevant, e.g., causing the subject to withdraw from the study, requiring treatment or causing apparent clinical manifestations, or judged relevant by the investigator, should be reported as an adverse event. Each event should be described in detail along with start and stop dates, severity, relationship to investigational product, action taken and outcome.

7.5.1.4 Reporting of serious adverse events

The definition of serious adverse events (SAEs) is given in Section 7.5.1.1.

Study investigators will be thoroughly instructed and trained on all relevant aspects of the investigator's reporting obligations for SAEs. This information, including all relevant contact details, is summarized in the investigator site file. This information will be updated as needed. All SAEs occurring during the observation period defined in Section 7.5.1.3 must immediately (within 24 hours of the investigator's awareness) be reported to Health Canada using the SAE

Phase II Study of Perindopril and Regorafenib in mCRC (PARICCA)

form, as well as to the Bayer Pharmacovigilance Department. Each SAE must be followed up until resolution or stabilization by submission of updated reports to the designated recipient.

SAEs occurring after the protocol-defined observation period will be processed by the investigator according to all applicable regulations.

In each case of a fatal or life-threatening reaction, the investigator must seek relevant follow-up information and must complete a follow-up report without delay to Bayer and Health Canada as described below.

For all SAEs, the investigator is required to document in full, the course of the SAE and any therapy given, including any relevant findings/records in the report.

It is not mandatory to report SAEs occurring after the protocol-defined observation period, however, at the investigator's discretion these may be reported if considered potentially relevant.

7.5.1.5 Responsibility for Reporting Serious Adverse Events to Bayer

Each Investigator will report to Bayer Inc. Pharmacovigilance department any SAE or AE of Special Interest within 24 hours of becoming aware of such event, in order to allow Bayer to process and/or submit such safety information according to the mandated timelines to health authorities worldwide.

Report event by email or fax to Bayer Inc. Pharmacovigilance:

BAYER SAE REPORTING NUMBER

[contact]

Email: [contact]

7.5.1.6 Prompt Reporting of SAEs to Health Canada

It is responsibility of the Sponsor of the study to report to Health Canada within 24 hours all serious adverse events (SAEs), as defined by applicable law or regulation regardless of attribution to the study drug and expectedness that are experienced by any Study subject receiving a study drug.

The Health Canada number for SAE reporting at the Marketed Health Products Directorate (MHPD):

[contact]

[contact]

E-mail: [contact]

Notification of the IECs / IRBs

Notification of the IECs / IRBs about all relevant events (e.g. SAEs, suspected, unexpected, serious adverse reactions (SUSARs)) will be performed by the investigator according to all applicable regulations.

Notification of the authorities

The processing and reporting of all relevant events (e.g. SAEs, SUSARs) to the authorities will be done by the investigator according to all applicable regulations.

7.5.1.5 Expected adverse events

The most frequently observed adverse drug reactions ($\geq 30\%$) in patients receiving regorafenib are described in the Stivarga[®] (regorafenib) Product Monograph and include asthenia/fatigue, hand-foot skin reaction, diarrhea, decreased appetite and food intake, hypertension, dysphonia and infection.

The most serious adverse drug reactions in patients receiving regorafenib are severe liver injury, hemorrhage, cardiac ischemia/infarction, hypertension, reversible posterior leukoencephalopathy syndrome (RPLS), Stevens-Johnson syndrome/toxic epidermal necrolysis, and gastrointestinal perforation or fistula). Of these, hypertension and hemorrhage have been observed most frequently.

The most frequent adverse reactions observed with perindopril are described in the COVERSYL[®] Product Monograph and include: cough, dizziness, headache, asthenia, gastro-intestinal disorders (abdominal pain, nausea, dyspepsia).

The most serious adverse reactions from perindopril are: hypersensitivity reaction (angioedema), renal dysfunction (in high risk patients), pancreatitis, blood disorders (pancytopenia, agranulocytosis, and thrombocytopenia).

During the long-term safety assessment in heart failure patients, the severe adverse events occurring with the highest frequency were angina pectoris and orthostatic hypotension.

The most severe drug reactions from post-marketing experience were pancreatitis and blood disorders (pancytopenia, agranulocytosis, and thrombocytopenia).

7.5.1.6 Adverse events of special safety interest

Regorafenib is an investigational drug and current knowledge of the adverse events associated with this compound is limited.

Phase II Study of Perindopril and Regorafenib in mCRC (PARICCA)

As with any new chemical entity, there is always potential for unexpected adverse events, including hypersensitivity reactions.

Based on data from Phase I/II studies with regorafenib and from current knowledge of the pharmacological properties of other small molecule TKIs in this drug class, as soon as there is reasonable suspicion of any of the following AEs, the investigator should immediately notify Bayer as outlined in section 7.5.1.4. These events are:

- Acute renal failure (CTC AE Grade 3) or severe proteinuria (CTC AE Grade 3)
- Interstitial lung disease
- Acute cardiac failure
- Clinically significant bleeding (CTCAE Grade 3)
- Stevens Johnson Syndrome
- Erythema multiforme

7.5.2 Pregnancies

The investigator must report to the sponsor any pregnancy occurring in a study subject, or in his partner, during the subject's participation in this study. The report should be submitted within the same timelines as an SAE, although a pregnancy per se is not considered an SAE.

For a study subject, the outcome of the pregnancy should be followed up carefully, and any abnormal outcome of the mother or the child should be reported.

For the pregnancy of a study subject's partner, all efforts should be made to obtain similar information on course and outcome, subject to the partner's consent.

For all reports, the forms provided are to be used.

7.5.3 Further safety

An isolated laboratory abnormality that is assigned grade 4, according to CTC definition, is not reportable as an SAE; unless the investigator assesses that the event meets standard ICH criteria for an SAE. CTC grade 4 baseline laboratory abnormalities that are part of the disease profile should not be reported as an SAE, specifically when they are allowed or not excluded by the protocol inclusion/exclusion criteria. If an investigator is in doubt about the applicable reporting obligations, he/she should consult with the study monitor for the Sponsor. CTC grade 4 lab abnormalities will be documented in the lab data and will be reviewed on a regular basis.

8. Statistical methods and determination of sample size

8.1 General considerations

Statistical analyses will be performed using SAS 9.3. Demographic and other baseline characteristics will be listed and summarized. Qualitative data will be summarized using frequencies and percentages and quantitative data will be summarized by appropriate descriptive statistics (mean, standard deviation, median, minimum and maximum). Secondary safety variables will be summarized using descriptive statistics and exploratory graphical presentations of the data.

Duration of study treatment exposure, cumulative dose and dose intensity will be summarized. The number of patients with dose changes/interruptions and withdrawals will be presented along with reasons for the dose change.

Variables related to tumor response and disease progression will be evaluated based on investigator assessed RECIST criteria, version 1.1. In cases where radiographic imaging is not possible, clinical progression may be used. Clinical progression is based on the judgment of the investigator.

Toxicity related variables will be evaluated using the CTCAE v4.03 criteria.

Biomarker and pharmacokinetics will not be performed in this study and no subgroup analysis will be performed.

8.2 Analysis sets

The primary analysis set will consist of all evaluable patients. An evaluable patient is defined as a patient who meets all inclusion/exclusion and who has received at least one dose of study medication. The safety set will consist of all patients who receive at least one dose of study medication.

8.3 Primary Objective

The primary objective is to determine the proportion of patients that have any grade HFSR toxicity when treated with a combination of regorafenib and perindopril.

8.3.1 Primary Endpoint

The primary endpoint of this study is proportion of patients with any grade HFSR toxicity. Toxicities will be evaluated used CTCAE v4.03 criteria.

8.3.2 Statistical hypothesis and method of analysis

The primary analysis will be a comparison of the proportion of patients with any grade HFSR toxicity to 47% using the normal approximation z-test statistic and 2-sided 5% significance level. The statistical hypotheses are

H0: $P = 0.47$ versus H1: $P \neq 0.47$

where P is the proportion of any grade HFSR toxicity.

The study includes a single interim safety analysis after 10 patients have completed the study medication.

The proportion of patients having worst grade 3 HFSR toxicity will be determined along with the 95% confidence interval.

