	
intensity will be summarized. The number of patients with dose changes/interruptions and withdrawals will be presented along with reasons for the dose change.
 
Variables related to tumor response and disease progression will be evaluated based on investigator assessed RECIST criteria, version 1.1. In cases where radiographic imaging is not possible, clinical progression may be used. Clinical progression is based on the judgment of the investigator.
 
Toxicity related variables will be evaluated using the CTCAE v4.03 criteria.
 
Biomarker and pharmacokinetics will not be performed in this study and no subgroup analysis will be performed.
 
Analysis sets
 
The primary analysis set will consist of all evaluable patients. An evaluable patient is defined as a patient who meets all inclusion/exclusion and who has received at least one dose of study medication. The safety set will consist of all patients who receive at least one dose of study medication.
 
Primary Objectives
 
The primary objective is to determine the proportion of patients that have any grade HFSR toxicity when treated with a combination of regorafenib and perindopril.
 
Secondary Objectives
 
The secondary objectives are to evaluate the time to development of worst (grade 3) HFSR toxicity, proportion of all grades of hypertension, proportion of all grade toxicities and progression-free survival. All toxicities will be evaluated using CTCAE v4.03.
 
Sample Size
 
The alpha level is 0.05 and the power is 80% for the sample size calculation. A total of 34 evaluable patients be needed. 38 patients will be recruited to account for inevaluable patients. The primary endpoint is a 50% reduction in all grades of HFSR based on CTCAE v4.03 criteria (from 47% of patients with any grade of HFSR down to 24% of patients).

--	--

CONTENTS

Synopsis	3
CONTENTS	10
List of abbreviations.....	13
1.0 Introduction	16
1.1 Background	16
1.2 Overview of regorafenib	16
1.3. Overview of perindopril	17
1.4 Hand foot skin reaction,.....	18
1.5 Rationale for Use in Colorectal Cancer	18
1.6 Clinical experience with Regorafenib	19
2. Study objectives	19
2.1 Primary outcome	19
2.2 Secondary outcomes.....	19
3. Investigators and other study participants	20
3.1 Data Monitoring Committee.....	20
3.2 Clinical Trials Nurse Coordinator (CTNC)	20
3.3 Clinical Trials Data Coordinator (CTDC)	20
3.4.1 Biostatistician	21
3.5 Location of laboratory and imaging facilities	21

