8.6 Planned interim analyses

A single interim analysis is planned to be performed at the point that 10 patients have completed their first cycle of study treatment. This will be to determine if the study should continue. The study will be discontinued if 5 out of the first 10 patients exhibit a Grade 3 HFSR. The lower bound limit of the 95% confidence interval would be 18.7% which is higher than the 17% of patients who experienced HFSR grade 3 severity in the CORRECT trial.

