8.7 Determination of sample size

A sample size of 34 patients achieves 80% power to detect a 50% reduction in all grades of HFSR toxicity (from 47% as seen in the CORRECT trial to 24%) using the normal approximation to the binomial distribution and a 2-sided 5% significance level.

9. Data handling and quality assurance

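### With 34 evaluable patients the primary z-test has a true two-sided type I error of 5.7%, not the stated 5%; its power is adequate, but its verdict at exactly 10/34 depends on the approximation

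*Combined protocol and SAP*

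**What the plan says.** Section 8.3.2 makes the primary analysis a test of the any-grade HFSR proportion against "47% using the normal approximation z-test statistic and 2-sided 5% significance level", with a two-sided alternative. It does not say whether the standard error is taken at the null value or at the observed proportion, and it gives no rejection counts.

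Section 8.7 states: "A sample size of 34 patients achieves 80% power to detect a 50% reduction in all grades of HFSR toxicity", from 47% to 24%, "using the normal approximation to the binomial distribution and a 2-sided 5% significance level". The Synopsis (Sample Size) repeats the targets: "The alpha level is 0.05 and the power is 80% for the sample size calculation". It adds that "38 patients will be recruited to account for inevaluable patients", so the number analysed may lie anywhere from 34 to 38.

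The one interim look (8.6) is a safety rule on grade 3 HFSR: "The study will be discontinued if 5 out of the first 10 patients exhibit a Grade 3 HFSR". It has no efficacy boundary and spends none of the primary 5%.

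**The concern.** The primary result is a count out of about 34, which moves in steps of one patient. A normal-approximation test at a nominal 5% rejects on a fixed set of counts, and the exact probability of that set under a 47% rate need not be 5% or less. If it exceeds 5%, the stated level is not a property of the named test at the planned size, and a benefit could be declared on a count that an exact test would not call significant. This is the trial's only hypothesis test, so the level quoted for it should be true.

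**Working it through.** **Inputs.** Null rate 0.47, two-sided 5%, z-test (8.3.2). Alternative 0.24, n = 34, 80% power (8.7). Recruitment of 38 (Synopsis).

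**1. The plan's own figure.** The one-sample normal-approximation formula is

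n = [(1.960 × √(0.47 × 0.53) + 0.842 × √(0.24 × 0.76)) / (0.47 − 0.24)]²

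= [(0.978 + 0.359) / 0.23]² = 33.8, rounded up to 34.

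The approximate power at 34 is 80.2%. The figures in 8.7 reproduce.

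**2. Counts at which the z-test rejects, n = 34.** With the null standard error, z = (x/34 − 0.47) / √(0.47 × 0.53/34):

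- x = 10: z = −2.055, p = 0.040 (reject)
- x = 11: z = −1.711 (do not reject)
- x = 22: z = +2.07 (reject)

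The observed standard error gives the same rejection region at n = 34: 10 or fewer, or 22 or more.

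**3. True level and power of that region.**

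- Binomial(34, 0.47): P(X ≤ 10) = 2.84%, P(X ≥ 22) = 2.87%, sum 5.71%.
- Binomial(34, 0.24): P(X ≤ 10) = 82.8%.

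**4. Alternatives at n = 34.**

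| Rule | Rejects at | True level | Power at 24% |
|---|---|---|---|
| Planned z-test | ≤10 or ≥22 | 5.71% | 82.8% |
| Exact, equal-tail | ≤9 or ≥23 | 2.40% | 71.3% |
| Exact, minimum-likelihood | ≤9 or ≥22 | 4.05% | 71.3% |
| Fixed counts | ≤10 or ≥23 | 2.84% + 1.23% = 4.07% | 82.8% |

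**5. The count that decides.** For benefit, the z-test and the two standard exact tests differ only at 10/34. There the z-test (null standard error) gives p = 0.040, the exact two-sided p is 0.057, and the exact 95% interval is 15.1% to 47.5%, which contains 47%. If the true rate is 24%, the probability of exactly 10 events is 82.8% − 71.3% = 11.5%. At 9/34 the exact p is 0.016, so all the rules agree.

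**6. Other evaluable numbers.**

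| Evaluable n | z-test level, null SE | z-test level, observed SE | Equal-tail exact test: power at 24% |
|---|---|---|---|
| 34 | 5.7% | 5.7% | 71.3% |
| 35 | 4.1% | 6.6% | 80.0% |
| 36 | 6.5% | 6.5% | 77.1% |
| 37 | 4.7% | 4.7% | 84.4% |
| 38 | 5.1% | 7.3% | 81.9% |

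The choice of standard error makes no difference at 34, 36 or 37, but it does at 35 and 38. Exact power does not rise steadily with n, because the rejection count moves in whole patients.

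**The case against.** The strongest reply is that nothing has been miscalculated. The plan declares a normal approximation for both sample size and analysis, the two agree, and the formula returns 34. A gap between nominal and exact level is a known feature of such tests. Here it is 0.7 points and affects one benefit count, whose probability under the null is only 2.84% − 1.18% = 1.7%. The exact p of 0.057 belongs to a test that the plan does not name. All of this stands, and it limits the point to a modest one.

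It does not remove the point. Section 8.3.2 states a 5% level for a named test which, at the planned number, has a level of 5.7%. The approximation is also not used throughout: the 18.7% lower limit quoted in 8.6 for 5 of 10 patients is the exact binomial limit.

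A reader might go further and infer that 5% and 80% cannot both be had with 34 patients, or that the trial is underpowered at 71%. The documents support neither. The 71% belongs to exact tests that are not planned, while the planned test has 82.8%. Rejecting at 10 or fewer or at 23 or more keeps the total two-sided error at 4.1% with the same 82.8%. The two targets conflict only if each tail is held to 2.5%, which 8.3.2 does not require, or if the minimum-likelihood exact test is chosen.

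**Conclusion.** The concern holds in a limited form. With 34 evaluable patients the z-test in 8.3.2 has a true two-sided type I error of 5.7% against a stated 5%. Its power at 24% is 82.8%, so power is not short. The sample size in 8.7 is correct by its own method. In practice, the benefit conclusion at 10/34 depends on the approximation, and that outcome has about an 11.5% chance if perindopril works as assumed. The unstated standard error is a second, smaller gap, which matters if 35 or 38 patients are evaluable.

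These figures assume independent patients, a fixed null of 47%, an alternative of 24%, and no effect of the safety look on the primary test. That look was not modelled.

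**What to change.** In 8.3.2, before analysis, specify one of the following.

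- **(a) Exact test.** An exact two-sided binomial test of P = 0.47 with an exact confidence interval, naming the construction (for example, equal-tail). Restate power at 24% by evaluable number in 8.7 and the Synopsis: 71% at 34, 80% at 35, 77% at 36, 84% at 37, 82% at 38.
- **(b) Fixed rejection counts.** Counts listed for each possible evaluable number, holding the total two-sided error at or below 5%. At 34: 10 or fewer, or 23 or more (level 4.1%, power 82.8%). State that the benefit tail is 2.84%.

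If the z-test is kept unchanged, state which standard error it uses and give its true level as 5.7% at 34.

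The cost is SAP wording and one line of code, with no patients beyond the 38 already planned. Under (a), the stated power at exactly 34 falls to 71%, and 34 is the number to expect if the recruitment allowance is used up. Under (b), the tails are unequal, and a reader who expects 2.5% for benefit will notice.

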8.4.2 Progression-free survival

Progression-free survival is defined as the time (days) from start date of study drugs to date of first documented disease progression (radiological or clinical) or death due to any cause, if death occurs before progression is documented. The actual date that the tumor scan was performed will be used for this calculation. Progression-free survival for patients without disease progression or death at the time of the final analysis will be censored at the last date of tumor evaluation. Progression-free survival for patients who have no tumor assessments after baseline will be censored at 1 day. Missing or non-evaluable tumor assessments will not be taken into account in the calculation of PFS. Every effort will be made to obtain radiologic imaging for documentation of progression. In those cases where patients are unable to obtain radiologic examinations due to deterioration of medical condition, the date of clinical progression will be used for the determination of the date of progression. The PFS distribution will be presented descriptively using Kaplan-Meier curves. The median PFS from the Kaplan-Meier distribution will be determined along with the associated 95% confidence interval.

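### Must 8.3.2 spell out the standard error and continuity correction of the primary z-test, and plan an interval for the any-grade HFSR proportion?

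*Combined protocol and SAP*

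**What the plan says.** Section 8.3.2 tests P = 0.47 against a two-sided alternative, "using the normal approximation z-test statistic and 2-sided 5% significance level". It gives no formula for the statistic and does not mention a continuity correction. Section 8.7 derives 34 patients for 80% power to detect a fall from 47% to 24%, "using the normal approximation to the binomial distribution and a 2-sided 5% significance level".

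On the denominator, Section 8.2 states: "The primary analysis set will consist of all evaluable patients". The Synopsis, under Sample Size, asks for 34 evaluable patients and adds: "38 patients will be recruited to account for inevaluable patients". Its Number of subjects row instead attributes the 38 to screen failures. Section 2, Section 7.5.1.2 and the Synopsis methodology give N = 34 as the HFSR denominator.

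On estimation, Section 8.3 states: "The primary objective is to determine the proportion of patients that have any grade HFSR toxicity". Intervals are planned elsewhere. Section 8.3.2 says "The proportion of patients having worst grade 3 HFSR toxicity will be determined along with the 95% confidence interval", and Section 8.4.2 says "The median PFS from the Kaplan-Meier distribution will be determined along with the associated 95% confidence interval". Section 8.6 quotes a 95% lower limit in support of the interim rule. For categorical data in general, Section 8.1 asks for frequencies and percentages.

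**The concern.** A one-sample z-test for a proportion can put either the null value or the observed proportion in its standard error, and can be used with or without a continuity correction. With about 34 patients these versions can disagree for a result near the boundary. The trial is open-label and single-arm, so a choice left until the data are in could decide whether a borderline result counts as a reduction. The number analysed may also differ from 34, which changes the boundary.

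The second worry is one of balance. The primary objective is to estimate a proportion, yet intervals are promised for grade 3 HFSR and median PFS and not for that proportion. A reader might be left with a p-value and no statement of precision.

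**Working it through.** **Inputs.** Null proportion 0.47, two-sided 5% level (8.3.2); alternative 0.24, 80% power, n = 34 (8.7). Normal quantiles 1.96 and 0.8416.

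**Step 1: reproduce the plan's sample size.** With the null standard error in the test and no correction:

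n = [1.96 × √(0.47 × 0.53) + 0.8416 × √(0.24 × 0.76)]² / 0.23² = 33.82, rounded up to 34.

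Power at 34 = Φ[(0.23 − 1.96 × √(0.47 × 0.53/34)) / √(0.24 × 0.76/34)] = 80.2%. The stated figures are reproduced.

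**Step 2: try the other versions.**

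- Standard error at 24% throughout: (1.96 + 0.8416)² × 0.24 × 0.76 / 0.23² = 27.06, so 28.
- Null standard error with continuity correction: (33.82/4) × [1 + √(1 + 2/(33.82 × 0.23))]² = 38.05, so 39.
- Null standard error in both terms: 36.96, so 37.
- Null standard error, one-sided: 26.34, so 27.

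None of these gives 34. Section 8.7 therefore identifies the null standard error without correction.

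**Step 3: decisions at n = 34.** For 10/34 (29.4%), the difference from 0.47 is 0.1759, the null standard error is 0.0856 and the observed one is 0.0781. The correction is 1/68 = 0.0147.

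| Version | z | p |
|---|---|---|
| Null, uncorrected | 2.055 | 0.040 |
| Null, corrected | 1.883 | 0.060 |
| Observed, uncorrected | 2.251 | 0.024 |
| Observed, corrected | 2.063 | 0.039 |

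At 9/34 all four versions reject (largest p = 0.026), and at 11/34 none does (smallest p = 0.068). Ten events is the only low-side count in dispute, and only the corrected null version dissents. On the high side the same version needs 23 events where the others need 22. The probability of exactly 10/34 is 0.0284 − 0.0118 = 1.7% at a true rate of 47%, and 0.828 − 0.713 = 11.5% at 24%.

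**Step 4: other denominators.** The range 32 to 38 is an assumption. Largest count showing a reduction:

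| n | Null, uncorrected (exact two-sided size) | Observed, uncorrected | Null, corrected |
|---|---|---|---|
| 32 | 9 (5.0%) | 9 | 9 |
| 33 | 9 (3.5%) | 10 | 9 |
| 34 | 10 (5.7%) | 10 | 9 |
| 35 | 10 (4.1%) | 11 | 10 |
| 36 | 11 (6.5%) | 11 | 10 |
| 37 | 11 (4.7%) | 11 | 10 |
| 38 | 11 (5.1%) | 12 | 11 |

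Some version differs by one patient at each n from 33 to 38, but two separate choices are at work. The standard error matters at 33, 35 and 38; the correction to the null version matters at 34, 36 and 37. The observed standard error with correction gives the same low-side limit as the null uncorrected version at every n in the table.

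**Step 5: the interval.** The Wilson interval inverts the null-standard-error z-test, so the two always agree. For 10/34, centre = (0.2941 + 1.96²/68)/(1 + 1.96²/34) = 0.315 and half-width = 0.147, which gives 16.8% to 46.2%. It excludes 47%, as p = 0.040 requires. For 11/34 it is 19.1% to 49.2%, which includes 47% (p = 0.087). It needs only the count and the denominator.

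**The case for a change.** The strongest argument for a change is that inference is not prespecification. The test is one clause short of complete, the trial is open-label, and under Section 3.4.1 the biostatistician reports to the Principal Investigator. If a correction were added, exact power at 34 patients and a 24% rate would fall from 82.8% to 71.3%. At 12/38, the null standard error gives p = 0.057 and the observed one 0.041. These figures are correct. But each reversal requires a departure from what the plan contains: a correction it does not mention, or a standard error that does not yield its sample size. Such a departure would be visible to anyone who compared the report with Section 8.7. The 12/38 example also needs all 38 recruits to be evaluable, while the Synopsis intends some as allowance for screen failure, and Section 5.2.1 defines those as patients who never start the drug.

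On the interval, the limit quoted in Section 8.6 (18.7% for 5/10) is the exact Clopper-Pearson value. Applied to 10/34, that method gives 15.1% to 47.5%, which includes 47% although the z-test rejects. That mismatch is real at this count, but Section 8.3.2 makes the z-test the primary analysis, so the verdict is not in doubt. It remains true that the plan promises no interval for its primary proportion. Adding one would be good reporting, but it would not alter the analysis.

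Section 7.3 refers to a statistical analysis plan for the list of variables, and no separate text of it is available. It might hold these details, but nothing here relies on that.

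**Conclusion.** No change follows. Section 8.3.2 leaves its formula unwritten, but the calculation in Section 8.7 supplies it: null standard error, no continuity correction. An analyst who works from the plan would reach that version and obtain a sound result. At 34 patients the exposure is one low-side count (10 events) and one high-side count (22), and only if a correction is added that the plan does not mention. The exact size of the implied test varies around the nominal 5% with n, from 3.5% to 6.5% over 32 to 38 patients. That is ordinary for a normal approximation at this size.

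The absent interval is a reporting gap with no bearing on the decision, because the reported count and percentage are enough to compute one. The conclusion assumes that the primary test is run on the basis used for the sample size and that the evaluable number is near 34. If n differs, the same formula applies with the actual n.
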